1.17.2 Secondary outcome measures

- Serum electrolytes
- Acid base disturbances
- Post-operative complications
- Requirements for ICU
- Requirement for dialysis or hemofiltration
- Duration of ICU stay
- Hospital length of stay

FLUid intervention and **Renal Outcome Trial** in patients undergoing major surgery: an observational single-centred study (**FLURO TRIAL**). Version 2, 31st Mar 2014

ETHICS

1.18 Guiding principles

This study is to be performed in accordance with World Medical Association Declaration of Helsinki: Ethical principles for medical research involving human subjects (WMA 2008), the International Ethical Guidelines for Biomedical Research Involving Human Subjects (CIOMS 2002) and the National Statement on Good Practice in Human Research.

The research utilises information normally gathered during the course of the delivery of a currently recognised treatment and will maintain anonymity and privacy and can therefore be conducted in accordance with Australian Law and the National Statement.

1.19 Ethical and legal issues in this study

Patterns of practice in different hospitals are often idiosyncratic and unscientific²². Indeed, much of clinical medicine remains empirical and local medical opinion and supply of resources are often more important than science in determining how medical care is delivered²². Wide variations that characterise usual clinical practice often have no basis in science but may have important implications for patient outcomes. Where there are two distinct approaches being employed in different institutions, we believe that there is an ethical imperative to conduct research to establish which approach is best.

This study utilises a novel design in order to assess the relative effects of perioperative intravenous fluids therapy. This study is clearly an observational study on the basis of conventional guidelines. **Specifically, the study involves no departure from standard care and does not involve the collection of any data that are not already being collected for clinical and/or quality assurance purposes.**

In this study, whether or not the patients receive saline, Hartmann's solution or Plasmalyte as default crystalloid fluid therapies, will be determined by the treating clinicians. No controls will be placed on the use of colloidal fluid therapy, blood products (red blood cells, platelets, cryoprecipitate or fresh frozen plasma) or any other fluid non-crystalloid fluid intervention (e.g. dextrose, bicarbonate).

All patients in this study will receive standard perioperative care.

This study involves negligible risk.

1.20 Confidentiality of patient data

Patients will be allocated a unique study number. Study data will be obtained from routinely collected quality assurance and clinical information. Data entered into the study database will be identified by the unique study number only. The enrolment log and the study data will be kept separately.

FLUid intervention and **Renal Outcome Trial** in patients undergoing major surgery: an observational single-centred study (**FLURO TRIAL**). Version 2, 31st Mar 2014

DATA MANAGEMENT

1.21 Data collection methods

The demographic, biochemical, and outcome data used in this study are already collected by the Austin Hospital for administrative and quality assurance purposes⁷.

Any ICU data are similarly collected and already provided to the Australian and New Zealand Intensive Care Society Centre for Outcome and Resource Evaluation as part of a government-funded bi-national quality assurance programme.

The only data used in this study, which are not routinely collected for quality assurance purposes, are the daily volume of study fluid administered as fluid boluses and the data relating to renal outcomes. These data will be collected by the Principle and Associate investigators.

1.22 Data management

De-identified data management will be performed by the Australian and New Zealand Intensive Care Research Centre (ANZIC-RC) located within the School of Epidemiology and Public Health of Monash University.

1.23 Protocol deviation

A protocol deviation is generally an unplanned excursion from the protocol that is not implemented or intended as a systematic change. The principle investigators will be responsible for ensuring the study is conducted in accordance with the procedures and evaluations described in this protocol and will protect the rights, safety, and welfare of all subjects. The principle investigator will not implement any deviation from, or changes of, the protocol, unless it is necessary to eliminate an immediate hazard to trial subjects.

For the purposes of this protocol, any deviations requiring notification to the Research Ethics Committee will be defined as any participant who

- Entered into the study even though they did not satisfy the entry criteria.
- Developed exclusion criteria during the study and not withdrawn.

When a deviation from the protocol is identified for an individual subject, the chief investigator will assess the deviation and the possible impact to the safety and/or efficacy of the subject to determine the continuation in the study. If a deviation impacts the safety of a subject, the principle investigator will inform the Research Ethics Committee in accordance with normal Hospital processes.

SAFETY CONSIDERATIONS

1.24 Adverse Events and Other Safety Aspects

Safety will be assessed throughout the study. As part of normal hospital care for all patients undergoing surgery at Austin Hospital, a complete baseline profile of each subject will be established by the treating surgical unit through medical history, clinical laboratory values, vital signs, physical assessments, and ECGs. During the course of the study, surgical and anaesthesia care, including vital signs, complete and targeted physical assessments, laboratory tests, and ECGs will be performed at in accordance with normal hospital protocols. **There will be no deviation from standard care at any time point.**

All medical and surgical changes from baseline will be monitored throughout the study by the treating units and appropriate interventions will be taken accordingly.

STATISTICAL CONSIDERATIONS

1.25 Power calculations and sample size

A recently published open label sequential period study of chloride-liberal vs. chloride-restrictive fluid administration² demonstrated a reduction in the incidence of injury and failure based on RIFLE criteria from 14% (95% CI, 11% - 16%) to 8.4% (95% CI, 6.4% - 10%); $P < 0.001$) with the introduction of a chloride-restrictive fluid regime.

Assuming that, as we have conservatively estimated, we can study 400-600 subjects over a 6-week period, our sample size will provide more than 90% power with an alpha of 0.01 to detect a difference of this magnitude between patients treated with saline vs. patients treated with different crystalloid fluids.

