1.3 Coordinating Department

Department of Anaesthesia
Austin Hospital
Heidelberg, Victoria
Australia

STUDY SYNOPSIS

Title:	Fluid intervention and Renal Outcome Trial in patients undergoing major surgery: an observational single-centred study (FLURO Trial).
Short Title:	Fluid therapy in major surgery.
Design:	Single-centred, prospective observational study. Information about intravenous fluid intervention (type of fluid and amount) for adult patients undergoing major surgery (duration >2 hours and at least one overnight stay) will be collected over a 6-week period. The effects of these fluids on renal function will be investigated.
Study Centers:	1
Hospital:	Austin Hospital
Study question:	What are the association between perioperative intravenous fluids and renal function in adult patients undergoing major surgery at a University teaching hospital.
Study Objectives:	To determine the association between perioperative intravenous fluids and renal function in adult patients undergoing major surgery.
Primary Outcome:	Acute kidney injury (AKI), defined by an increase in creatinine greater than 25% or 0.5 mg/dL (44 µmol/L) from baseline to peak value within the first 72-hours postoperatively.
Secondary Outcomes:	Serum electrolytes Acid base disturbances Post-operative complications Requirements for ICU Requirement for dialysis or hemofiltration Duration of ICU stay Hospital length of stay In-hospital mortality
Inclusion criteria:	Adult patients ≥ 18 years Elective or emergency surgery Surgery duration > 2 hours Requiring at least one overnight stay
Exclusion criterion:	<18 years in age Liver transplantation
Number of planned Subjects:	400-600

FLUId intervention and **Renal Outcome Trial** in patients undergoing major surgery: an observational single-centred study (**FLURO TRIAL**). Version 2, 31st Mar 2014

Investigational product:	Nil
Safety considerations:	
This is an observational study only. There is no departure from standard care at any stage. It only involves the collection of data that has already been collected for clinical or quality assurance purposes.
 
Perioperative care and fluid intervention will remain completely at the discretion of the treating clinicians.

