1.6 Study design

This study aims to observe the association between perioperative intravenous fluids have and renal function in adult patients undergoing major surgery. **It is a single-centered, prospective observational study and therefore does not change the standard of care in any way.** All patients undergoing surgery at Austin Hospital will be given the perioperative fluids at discretion of the treating clinicians.

The study will be conducted over a 12-week period, allowing a wide variety of amount and type of fluids given to the patients. Austin Hospital staff specialists in anaesthesia agree that on the basis of current evidence, Saline (0.9%), Plasmalyte or Hartmann's solution are equally acceptable for crystalloid fluid therapy in every situation requiring major surgery with the exclusion of surgery for liver transplantation where specific hospital perioperative fluid protocols are used in these settings.

As there is no departure from standard care for this study, Saline (0.9%), Plasmalyte and Hartmann's solution will be available for administration to all patients undergoing major surgery. In the situations, where, in the opinion of the treating anaesthetist or clinician, there is a clinical indication for other types of fluid e.g. colloids, blood, dextrose etc, again there will be no deviation from standard care in any way.

All adult patients who undergo major surgery will be analysed. The primary outcome will be the proportion of patients with kidney injury or failure based on established criteria⁵. Secondary outcomes will include delta creatinine (the difference between baseline and peak creatinine), serum electrolyte levels, acid base disturbances, requirements for ICU, duration of ICU stay, hospital length of stay, complications and in-hospital mortality.

All of the data required for this study are collected routinely as part of standard clinical care and/or quality assurance activities⁶.

FLUid intervention and **Renal Outcome Trial** in patients undergoing major surgery: an observational single-centred study (**FLURO TRIAL**). Version 2, 31st Mar 2014

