1.9 Number of participants

Given the current theatre workload at Austin Hospital, 400-600 participants will be recruited.

FLOW DIAGRAM

RESEARCH QUESTION

What is the association between perioperative intravenous crystalloids with renal function in adult patients undergoing major surgery at a University teaching hospital?

BACKGROUND AND RATIONALE

For all patients undergoing major surgery, two important and fundamental goals in fluid intervention include the maintenance of intravascular volume to ensure optimal organ perfusion and function, and the avoidance of metabolic and electrolyte disturbances that can compromise organ function.

Worldwide, the most commonly used crystalloid fluids available for all patients undergoing surgery include:

1. Hartmann's solution
2. Saline (0.9%)
3. Plasmalyte solution

The electrolyte composition of some of these commonly used crystalloid fluids are summarised in Table 1. All these solutions have similar sodium concentrations (130-150 mmol/L) and may contain physiological concentrations of potassium (Hartmann's and Plasmalyte solutions). There are however some major differences in anion composition. All three solutions above have chloride as a major anionic constituent, the balance in Hartmann's and Plasmalyte solutions being made up of lactate and acetate respectively. Both lactate and acetate are ultimately metabolised by the liver to bicarbonate, thus producing a near ideal physiological solution. Because their electrolyte composition is similar to plasma, they are frequently called "balanced" crystalloid solutions.

Pre-clinical and early clinical data suggest that saline may give rise to adverse effects including immune dysfunction⁷, gastrointestinal dysfunction⁸ and decreased renal cortical perfusion and renal blood flow⁹. There is strong expert opinion that 'normal saline' or Saline (0.9%) is neither "normal" nor "physiological"¹⁰. In fact, it has approximately 1.5 times more chloride than normal plasma and its use can lead to hyperchloraemic acidosis³. Although hyperchloraemic acidosis may be a benign phenomenon^{11,12}, recent data raise the possibility that the use of saline for fluid resuscitation in adult ICU patients may lead to an increased risk of developing acute kidney injury compared to resuscitation fluids with a lower concentration of chloride such as Plasmalyte^{2,13}.

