1.10 Summary

This is an observational study; there is no departure from standard care at any stage. It involves the collection of data that has already been collected for clinical or quality assurance purposes.

In this study we will be collecting information about intravenous fluid intervention (type of fluid and amount) for adult patients undergoing major surgery (duration >2 hours and at least one overnight stay). Data will be collected over a 12-week period. Specifically, the association of these fluids with kidney function will be investigated. Perioperative care and fluid intervention therefore will remain completely at the discretion of the treating clinicians.

The current study will inform clinicians looking after patients undergoing major surgery about the effects of these fluids on renal injury.

This study will be also be used in Fulfilment of University of Melbourne BSc Honours Project for [name].

FLUid intervention and **Renal Outcome Trial** in patients undergoing major surgery: an observational single-centred study (**FLURO TRIAL**). Version 2, 31st Mar 2014

OBJECTIVES

The overall objective of this study is to determine the association between perioperative intravenous fluids and renal function in adult patients undergoing major surgery.

The choice of perioperative intravenous fluid intervention such as Saline (0.9%) vs. Plasmalyte vs. Hartmann's solution will be entirely at the discretion of the all clinicians caring for the patients.

Specifically, we aim to establish the association of Saline (0.9%), Plasmalyte and Hartmann's solution on:

1. The development of acute kidney injury in hospital
2. The development of biochemical and acid-base derangements
3. The development of postoperative complications
4. Requirements for ICU
5. Requirement for dialysis or hemofiltration
6. Duration of ICU stay
7. Hospital length of stay
8. Hospital mortality

STUDY DESIGN

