1.17 Treatment allocation

Non-applicable. There is no departure from standard care at any stage. It only involves the collection of data that has already been collected for clinical or quality assurance purposes.

Total study duration: 12 weeks

TREATMENT SCHEME

All adult patients (≥ 18 years) undergoing major surgery (> 2 hours) and requiring at least one overnight post-operative hospital stay:

Outcome measures

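### The data-collection period is 6 weeks in two places and 12 weeks in four, and the protocol does not say whether the calendar or the 400-600 target ends enrolment

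*Protocol*

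**What the plan says.** Six places in the protocol give a period:

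| Place | Period | Text |
|---|---|---|
| Study Synopsis, Design row | 6 weeks | "will be collected over a 6-week period" |
| 1.25 Power calculations and sample size | 6 weeks | "we can study 400-600 subjects over a 6-week period" |
| Lay Summary | 12 weeks | same statement as in 1.10 |
| 1.6 Study design | 12 weeks | "The study will be conducted over a 12-week period" |
| 1.10 Summary | 12 weeks | "Data will be collected over a 12-week period" |
| 1.17 Treatment allocation | 12 weeks | "Total study duration: 12 weeks" |

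The planned number is 400-600 in the synopsis, in 1.9 ("400-600 participants will be recruited") and in 1.25. Section 1.9 bases it on theatre workload and attaches no period. Section 1.25 attaches it to 6 weeks and calls the estimate conservative. None of the four 12-week statements gives a number.

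Section 1.25 then claims "more than 90% power with an alpha of 0.01" for a difference of 14% versus 8.4% between saline and other crystalloids.

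**The concern.** The study takes every eligible adult at one hospital, so its size is the accrual rate multiplied by the time enrolment stays open. The protocol gives two values for that time and one range for the product. The two periods cannot both fit that range at the same accrual rate.

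Three things are at stake:

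- The power statement in 1.25 rests on the shorter period, while most of the design text uses the longer.
- No rule closes enrolment. A stop at week 6, at week 12, or on reaching some number between 400 and 600 could each be defended from the text. Under 1.21 the investigators themselves collect the fluid volumes and renal outcomes, and under 1.29 there is no blinding, so the end point should not be left open.
- The synopsis and 1.26 tie finalisation of the statistical analysis plan to the end of data collection or of the study, so that deadline moves with the unresolved date.

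**Working it through.** **1. Can the two periods describe different things?** One might read 6 weeks as enrolment and 12 weeks as enrolment plus follow-up. The synopsis, the lay summary and 1.10 rule this out: each gives the period over which data on fluid type and amount are collected, for the same patients.

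**2. Implied accrual** (number divided by weeks)

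- 6 weeks: 400/6 = 67 and 600/6 = 100 per week.
- 12 weeks: 400/12 = 33 and 600/12 = 50 per week.

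The two differ by a factor of two.

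**3. Expected number if the calendar ends enrolment**

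- 6-week rate run for 12 weeks: 2 × (400 to 600) = 800 to 1,200.
- 12-week rate run for 6 weeks: (400 to 600)/2 = 200 to 300.

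**4. The plan's own power figure.** Inputs from 1.25 are p1 = 0.14, p2 = 0.084 (difference 0.056) and alpha 0.01. Sidedness and group sizes are not given, so I take a two-sided test and an equal split as the main case. With n per group and mean proportion 0.112:

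- SE0 = sqrt(2 × 0.112 × 0.888 / n)
- SE1 = sqrt((0.14 × 0.86 + 0.084 × 0.916) / n)
- power = Φ((0.056 − 2.576 × SE0) / SE1)

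For N = 400 (n = 200), SE0 = 0.03154 and SE1 = 0.03141. Power = Φ((0.056 − 0.08123)/0.03141) = Φ(−0.80) = 21%. The other totals follow in the same way:

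| Total N | Two-sided 0.01, 1:1 | One-sided 0.01, 1:1 | Two-sided 0.01, saline:other 1:2 / 1:3 / 2:1 |
|---|---|---|---|
| 400 | 21% | 29% | 22% / 20% / 15% |
| 600 | 34% | 44% | 34% / 30% / 26% |
| 800 | 47% | 57% | 46% / 41% / 38% |
| 1,200 | 69% | 77% | 66% / 59% / 60% |

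The stated figure of more than 90% is not reproduced in any cell. For 90% power with an equal split, the total needed is about 1,884 two-sided or 1,648 one-sided, without continuity correction.

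**5. Precision.** The 95% half-width of the risk difference with an equal split is 1.96 × SE1:

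- N = 400: 6.2 points; N = 800: 4.4 points.
- N = 600: 5.0 points; N = 1,200: 3.6 points.

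Each doubling of N narrows the interval by sqrt(2) = 1.41.

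**The case against.** The strongest reply is that 400-600 is the same wherever a number appears, so the planned size is not in dispute and only the implied weekly rate changes. The synopsis and 1.9 can be read as setting a target. This stands as far as it goes. A reader might infer from the two periods that the planned size and precision differ by a factor of two, and the protocol does not support that. It nowhere plans 800-1,200. That figure needs both a calendar stop and a constant 6-week rate, and the opposite assumption gives 200-300. Even if N did double, interval width would change by 1.41; only the information doubles.

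The reply does not remove the problem, because the protocol does not make 400-600 a stopping rule either. Section 1.6 has all adult major-surgery patients analysed, 1.9 derives the number from workload, and 1.25 presents it as an estimate. A range whose top is 50% above its bottom cannot serve as a stopping count.

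A reader might also infer that the investigators intend to choose the end date after looking at the data. The protocol describes no interim look and no data-dependent stop. The ambiguity leaves that possible; it does not plan it.

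Finally, the power shortfall does not come from the two periods. It is present under either, and so does not measure the harm of the contradiction.

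**Conclusion.** The contradiction is certain: it stands in current text and has no reading that reconciles it. Its direct effect is an accrual assumption uncertain by a factor of two and an enrolment end that is not fixed. The effect on study size is conditional. If the calendar ends enrolment, the expected total could be 200-300, 400-600 or 800-1,200, depending on which rate and which period are right. If 400-600 is a true target, the size is unaffected and only the duration is in doubt.

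The power claim fails under both periods at the protocol's own rates and alpha: 21-34% at 400-600 and 47-69% at 800-1,200 with an assumed equal split. With splits of 1:2, 1:3 or 2:1 the ranges are 15-34% and 38-66%. A one-sided test does not reach 90% either.

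Severity is moderate. The target number, eligibility, outcome and analysis method do not depend on the period as written, and the correction is simple. It still matters, because the period is a basic design parameter on which 1.25 builds its sample size.

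**What to change.** - State one data-collection period in the synopsis, lay summary, 1.6, 1.10, 1.17 and 1.25. Four of the six already say 12 weeks.
- State what ends enrolment: a fixed calendar date or one fixed number, in either case regardless of accumulating data.
- Give the expected number that matches that rule in the synopsis, 1.9 and 1.25, with the weekly rate it assumes.
- Restate the power in 1.25 for that number, with the assumed saline:other split and the sidedness of the test. If the honest figure is well below 90%, say so, or give the expected interval width instead.

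The cost is protocol wording and one short recalculation. No new data are needed. Choosing 12 weeks would lengthen collection only relative to the two places that now say 6.

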1.26 Analysis plan

A complete description of the statistical analyses will be specified in a statistical analyses plan, finalised prior to completion of the study.

All analyses will be conducted on an intention-to-treat basis.

The primary analyses will be unadjusted analyses in which binary outcomes will be compared using relative risks with 95% confidence intervals and chi square tests and continuous outcomes will be compared with the use of mean differences and unpaired T-tests assuming that normality assumptions are met. If normality assumptions are not met then we plan to attempt simple data transformation, such as a logarithm transformation, and if this fails to proceed to a Mann-Whitney rank based test. Adjusted analyses will be performed using Poisson regression for binary

FLUid intervention and **Renal Outcome Trial** in patients undergoing major surgery: an observational single-centred study (**FLURO TRIAL**). Version 2, 31st Mar 2014

outcomes and linear regression for continuous outcomes. Baseline covariates will include age, gender, elective vs. emergency surgery, surgical specialty of admission, type of operation, and baseline serum creatinine level. Survival times will be compared using log-rank tests and presented as Kaplan-Meier curves. Multivariable models will be developed to study the predictors of AKI and the independent association between fluid choice and renal outcomes.

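### Section 1.25 claims more than 90% power at alpha 0.01 for 14% vs 8.4%, but its own inputs give about 21% to 34%

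*Protocol*

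**What the plan says.** Protocol section 1.25 takes its planning effect from a cited sequential-period study in which the incidence of RIFLE injury and failure fell "from 14% (95% CI, 11% - 16%) to 8.4% (95% CI, 6.4% - 10"%). It assumes that "we can study 400-600 subjects over a 6-week period" and concludes that "our sample size will provide more than 90% power with an alpha of 0.01 to detect a difference of this magnitude". The comparison is "between patients treated with saline vs. patients treated with different crystalloid fluids".

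The 400 to 600 is a total. The synopsis gives it as the planned number of subjects, and section 1.9 says: "Given the current theatre workload at Austin Hospital, 400-600 participants will be recruited".

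Under section 1.26 the primary analysis is unadjusted, with binary outcomes "compared using relative risks with 95% confidence intervals and chi square tests". The protocol gives neither the sidedness of the test nor the expected share of patients on saline. Fluid choice is left to the treating clinicians (section 1.16).

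**The concern.** A fall from 14% to 8.4% is 5.6 percentage points on a fairly uncommon binary outcome. Groups of 200 to 300 are far too small to detect that with 90% power, and a strict alpha of 0.01 makes it harder still.

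The Background gives a quick check. The cited study that supplied these rates had 1,533 patients. Even that number, split equally, would have about 82% power at two-sided alpha 0.01 for this effect. A study less than half that size cannot exceed 90%.

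The claim concerns the primary outcome, and it is the only statistical argument offered for the sample size. The study is also meant to inform the design and power calculations of a larger interventional trial (sections 1.5 and 1.7, and the end of the Background). A large overstatement of its own sensitivity weakens it for that purpose and makes it more likely that a non-significant result is over-read.

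**Working it through.** **Inputs from the protocol.** p1 = 0.14 and p2 = 0.084 (section 1.25); N = 400 to 600 in total (synopsis, sections 1.9 and 1.25); alpha = 0.01 (section 1.25); chi-square test (section 1.26).

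**Assumptions for the base case.** Two-sided test, equal groups of n = N/2. Both are varied below.

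**Formula (pooled variance under the null).** Power = Φ[(d − z·SE0)/SE1], where
- d = p1 − p2 = 0.056
- SE0 = √(2·p̄(1 − p̄)/n), with p̄ = 0.112, so 2·p̄(1 − p̄) = 0.198912
- SE1 = √((p1(1 − p1) + p2(1 − p2))/n), with p1(1 − p1) + p2(1 − p2) = 0.1204 + 0.076944 = 0.197344
- z = 2.576 for two-sided 0.01

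**Attempt to reproduce the stated figure (more than 90%).**
- N = 400, n = 200: SE0 = 0.03154, SE1 = 0.03141. (0.056 − 2.576 × 0.03154)/0.03141 = −0.803, so power = 21.1%.
- N = 600, n = 300: SE0 = 0.02575, SE1 = 0.02565. (0.056 − 2.576 × 0.02575)/0.02565 = −0.403, so power = 34.4%.

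The stated figure is not reproduced.

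**Could another reading explain it?**

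| Variant | N = 400 | N = 600 |
|---|---|---|
| Base case: two-sided 0.01, equal groups | 21.1% | 34.4% |
| Unpooled variance | 21.4% | 34.7% |
| Arcsine | 21.6% | 35.0% |
| Continuity-corrected | 16.8% | 29.7% |
| Best possible split (saline about 40% to 42%) | 22.2% | 35.3% |
| Saline one third | 21.8% | 33.9% |
| Saline 20% | 17.8% | 26.8% |
| Saline 80% | 7.8% | 14.2% |
| One-sided 0.01 | 29.0% | 44.0% |
| Two-sided 0.05 | 42.7% | 58.5% |
| One-sided 0.05 | 55.2% | 70.3% |
| N doubled to 800 / 1,200, two-sided 0.01 | 47.4% | 69.2% |
| Outer confidence limits, 16% vs 6.4%, two-sided 0.01 | 68.2% | 87.8% |

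The doubling row covers two cases: 400 to 600 read as a per-group number, and accrual that doubles because the lay summary and sections 1.6, 1.10 and 1.17 say 12 weeks where the synopsis and section 1.25 say 6. With the planning rates of 14% and 8.4%, the one variant tried that passes 90% changes both alpha and N: 600 per group at one-sided 0.05 gives 92.5%.

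**Sample size for 90% power.** n per group = (z·√0.198912 + 1.2816·√0.197344)²/d² = (2.5758 × 0.44600 + 1.2816 × 0.44423)²/0.003136 = 2.952/0.003136, which rounds up to 942. The total is 1,884, or 1884/600 = 3.1 to 1884/400 = 4.7 times the planned size.

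**What the planned size can do (equal groups).**
- 95% CI half-width for the risk difference: 1.96 × 0.03141 = 6.2 points at N = 400; 1.96 × 0.02565 = 5.0 points at N = 600.
- With 14% on saline, 90% power at two-sided 0.01 requires a comparator rate of about 3.2% at N = 400 or 4.8% at N = 600.

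**The case against.** **The endpoint differs from the one in the cited study.** The 14% and 8.4% are RIFLE injury and failure in critically ill patients. This study counts a creatinine rise above 25% or 44 µmol/L after major surgery, so its event rate may be higher. That stands as a limit: power under the real event rate is unknown, and 21% to 34% is power under the protocol's stated inputs only. It does not rescue the claim. Keeping the 5.6-point difference at a 20% saline rate lowers power to about 22% at N = 600. Keeping the ratio 8.4/14 = 0.6 would need a saline rate of about 35% or more at N = 600, and above 40% at N = 400, which the protocol nowhere assumes.

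**This is a preliminary observational study at negligible risk, with its size set by workload.** That is right, and such a study need not be powered. But this protocol does make a power claim, and the figure is wrong where it stands. A separate analysis plan would not correct it.

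Three stronger readings are tempting and not supported:
- A reader might infer that the power claim is the sole basis for the sample size. Section 1.9 rests the number on theatre workload.
- A reader might infer that the plan will treat a null result as evidence of no effect. No section says how a non-significant result will be interpreted. The overstatement raises that risk, and no more can be said.
- A reader might see a contradiction between alpha 0.01 in section 1.25 and the 95% intervals in section 1.26. A planning alpha stricter than the interval level is not a contradiction, and section 1.26 sets no test level.

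**Conclusion.** The stated power is wrong as written. Under the protocol's own rates, total size and alpha, with a two-sided test and equal groups assumed, power is about 21% to 34%. If the planning effect were fully real, the study would therefore miss it at the stated alpha in roughly 66% to 79% of repetitions. The conclusion does not depend on the two assumptions: no split lifts power above about 35% at N = 600, and one-sided testing reaches only 44%. A saline-heavy split would make it much worse, so 21% to 34% should not be quoted as the study's true power without its conditions. The error lies in the claim and does not show that the planned size is unsuitable for a preliminary study.

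**What to change.** Replace the power sentence in section 1.25. The new text should:

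1. State that feasibility (theatre workload, as in section 1.9) sets the 400 to 600.
2. Give the power for 14% vs 8.4% with its assumptions. For a two-sided test at alpha 0.01 this is about 21% to 34% with equal groups, 18% to 27% if saline is 20% of patients, and 8% to 14% if it is 80%. The sponsor should name the saline share it expects and keep a range around it.
3. Give the expected precision: a 95% CI half-width for the risk difference of about 6.2 points at 400 and 5.0 at 600, with equal groups.
4. Give the detectable difference: 90% power at two-sided alpha 0.01, with equal groups, only for about 14% vs 3.2% at 400 or 14% vs 4.8% at 600.
5. Align the section with the preliminary aim stated in the lay summary, section 1.7 and the Background, so that a non-significant result is not over-read.

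The cost is the rewording of one section and a less favourable stated figure. No more patients, data or analyses are needed.
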